5.2 Inclusion criteria

Patients eligible for inclusion in this study have to meet **all** of the following criteria:

Patient must meet the following laboratory values at the screening visit unless cytopenias are related to CLL:

1. Diagnosis of chronic lymphocytic leukemia (CLL) meeting criteria established in the World Health Organization (WHO) classification of hematologic disorders or International Workshop on Chronic Lymphocytic Leukemia (IWCLL) ([Hallek et al 2018](#)). Variant immunophenotype and prolymphocytic morphology change after diagnosis of CLL is allowed.
2. Age \geq 18 years
3. [REDACTED]
4. Male patients agree to avoid fathering a child as per the ibrutinib package insert

5. Dose escalation:
 - a. On ibrutinib > 1 year following relapse from another approved therapy without achieving a complete response

[figure not shown]
OR
 - b. On ibrutinib following relapse with another approved therapy and the presence of a known ibrutinib resistance mutation (BTK or PLC γ 2) at ≥ 1 variant allele frequency OR $< 1\%$ with two separate measurements at least 4 weeks apart with increasing variant allele frequency.
6. Dose expansion:
 - a. Arm A: On ibrutinib > 1 year following relapse from another approved therapy without achieving a complete response and patients who have received ibrutinib either alone or in combination (or have received ibrutinib continuously with multiple sequential combination partners) as first-line therapy and have failed to achieve a complete response after 1 year.
 - b. Arm B: On ibrutinib following relapse with another approved therapy and patients who have received ibrutinib either alone or in combination (or have received ibrutinib continuously with multiple sequential combination partners) as first-line therapy and the presence of a known ibrutinib resistance mutation at $\geq 1\%$ variant allele frequency OR $< 1\%$ with two separate measurements at least 4 weeks apart with increasing variant allele frequency. *Note: As of Amendment 6, patients will no longer be enrolled into Arm B.
7. Ibrutinib dose:
 - Escalation: Patients must be receiving 420 mg ibrutinib
 - Expansion: Patients may be on a dose of ibrutinib lower than 420 mg. Any dose must have been stable for 2 months prior to the start of study treatment.
8. Absolute Neutrophil Count ≥ 750 cells/ μ L ($0.75 \times 10^9/L$) independent of growth factor support within 7 days of the first dose of VAY736

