6.1.1 Dosing regimen

The dosing cycle is 28 days. Patients will receive ibrutinib once daily continuously and VAY736 by i.v. once every 2 weeks (Days 1 and 15). During the dose escalation part of the study, the dose of ibrutinib will be 420 mg. During the dose expansion part of the study, ibrutinib will be continued at the same dose schedule as tolerated before study enrollment, see exclusion criteria in [Section 5.2](#) for additional information on dose level.

A Q4W dosing schedule may also be evaluated if supported by emerging clinical data (e.g., safety or PK/PD or activity). The escalation of the Q4W dosing schedule will be guided by a separate BLRM. The DLT data available from VAY736 Q2W will be used to derive a MAP prior distribution for the Q4W dosing schedule as described in [Section 10.4.2](#). This decision will be formally documented in dose-escalation meeting minutes and distributed to all study sites.

Table 6-1 Dose and treatment schedule

Study treatments	Pharmaceutical form and route of administration	Dose	Frequency and/or Regimen
VAY736	Powder for solution for infusion	As assigned	Once every 2 weeks or every 4 weeks, as assigned
Ibrutinib	Solid dose (tablet or capsule) for oral use	Dose escalation: 420 mg Dose expansion: 420 mg or highest tolerated dose	Daily (28 day cycles)

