9.4 Database management and quality control

Novartis personnel, or designee, will review the data entered by investigational staff for completeness and accuracy. Electronic data queries stating the nature of the problem and requesting clarification will be created for discrepancies and missing values and sent to the investigational site via the EDC system. Designated investigator site staff are required to respond promptly to queries and to make any necessary changes to the data.

Concomitant treatments and prior medications entered into the database will be coded using the WHO Drug Reference List, which employs the Anatomical Therapeutic Chemical classification system. Medical history/current medical conditions and adverse events will be coded using the Medical dictionary for regulatory activities (MedDRA) terminology.

Samples and/or data will be processed centrally and the results will be sent electronically to Novartis (or a designated CRO).

After database lock, the investigator will receive copies of the patient data for archiving at the investigational site.

10 Statistical methods and data analysis

The data will be analyzed by Novartis and/or designated CRO. Any data analysis carried out independently by the investigator should be submitted to Novartis before publication or presentation.

It is planned that the data from participating centers in this protocol will be combined, so that an adequate number of patients will be available for analysis. Data will be summarized using descriptive statistics (continuous data) and/or contingency tables (categorical data) for demographic and baseline characteristics, efficacy measurements, safety measurements and all relevant pharmacokinetic and pharmacodynamics measurements.

Categorical data will be presented as frequencies and percentages. For continuous data, mean, standard deviation, median, minimum, and maximum will be presented.

Patients treated with the same dose level and schedule of VAY736 will be pooled into a single treatment group (includes patients from dose escalation and dose expansion parts) for all safety analysis.

For efficacy all analysis will be provided by dose level in dose escalation and by two arms in dose expansion.

Screen failure patients are those who signed the informed consent, but never started the study treatment for any reason. For these patients, the eCRF data collected will not be included in analyses, but will be reported in the CSR as separate listings.

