1.2 Study objectives and endpoints

Objectives and related endpoints are described in [Table 1-1](#) below.

Table 1-1 Objectives and related endpoints

Objective	Endpoint	Analysis
Primary		Refer to Section 2.6
To determine the MTD and/or RD of the combination of VAY736 with ibrutinib	Safety Escalation only: 
Incidence of DLTs in cycle 1 (28 days)	
To characterize the safety and tolerability of the combination of VAY736 and ibrutinib	Escalation and expansion: 
Incidence and severity of AEs and SAEs, including changes in laboratory parameters and vital signs Tolerability Dose interruptions, reduction, and dose intensity	
Secondary		Refer to Section 2.8
To assess any preliminary antitumor activity of the combination	Rate of patients with CR/CRI assessed by investigators per IWCLL at cycle 9 day 1 Overall response rate (ORR) assessed by investigators per IWCLL criteria and Time To Progression (TTP)	
	Clearance of ibrutinib resistance mutations (BTKC481 and/or PCLy2 hotspot), defined as less than 1% mutation bearing alleles (Arm B only).	
To characterize the PK of VAY736 and ibrutinib when used in combination therapy	Plasma concentration of VAY736 and ibrutinib, and derived parameters	
To assess immunogenicity (IG) following one or more intravenous infusions of VAY736	Presence of anti-VAY736 antibodies	

Objective	Endpoint	Analysis

2 Statistical methods

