A treatment is defined by the dose level (corresponding to a single combination of doses of VAY736 and ibrutinib) and regimen. During the initial dose-escalation phase of the study, in which the dose of VAY736 will be escalated in combination with a fixed dose of ibrutinib, cohorts of patients with the same treatment will be pooled into one single *treatment group*. Thus, a treatment group may consist of more than one cohort. Patients receiving the same dose of VAY736 under different regimens, Q2W or Q4W, belong to different treatment groups. Specific plans regarding a change in dosing regimen are discussed in [Section 2.6.1.1](#) of the SAP.

Patients treated with the same dose level and schedule of VAY736 will be pooled, for all safety analyses including PK and ADA, into a single treatment group (which may include patients from both the dose-escalation and dose-expansion parts).

For efficacy analyses, data will also be summarized by study part, and within each study arm of the dose expansion part. If multiple dose regimens are observed, summaries will also be produced within each treatment regimen as follows:

- Study parts: dose escalation, dose expansion
- Study arms:

- Dose expansion part:
 - Study arm A (~20 pts): patients with advanced CLL who have been on ibrutinib treatment for more than one year with evidence of residual disease and which places them at risk for clinical relapse.
 - Study arm B (~20 pts): patients with acquired resistance mutations to ibrutinib who have not yet demonstrated clinical relapse.

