2.8.4 Pharmacokinetic analysis

PK parameters will be determined using non-compartmental method(s) for VAY736 and ibrutinib. PK parameters such as those listed in [Table 2-7](#) will be estimated and reported, when applicable. For ibrutinib, PK parameters determined will be only AUClast, Cmax, Tmax, Tlast, and if applicable other PK parameters (eg AUC0-t). The PAS subset of patients will be used in all pharmacokinetic data analysis and summary statistics.

Table 2-7 Noncompartmental pharmacokinetic parameters

AUClast	The AUC from time zero to the last measurable concentration sampling time (tlast) (mass x time x volume ⁻¹)
AUCinf	The AUC from time zero to infinity (mass x time x volume ⁻¹)
AUCtau	The AUC calculated to the end of a dosing interval (tau) after first dose and at steady-state (amount x time x volume ⁻¹)
Cmax	The maximum (peak) observed plasma, blood, serum, or other body fluid drug concentration after single dose administration (mass x volume ⁻¹)
Tmax	The time to reach maximum (peak) plasma, blood, serum, or other body fluid drug concentration after single dose administration (time)
T1/2	The elimination half-life associated with the terminal slope (λ_z) of a semi logarithmic concentration-time curve (time). Use qualifier for other half-lives
CL/F	The total body clearance of drug from the plasma (volume x time ⁻¹)
Vz/F	The apparent volume of distribution during terminal phase (associated with λ_z) (volume)
Racc	Accumulation ratio should be calculated using AUC values obtained from a dosing interval

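### SAP 2.1 pools ibrutinib PK by VAY736 dose level and schedule, so groups with expansion patients may mix ibrutinib doses, against its own definition of a dose level

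*SAP*

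**What the plan says.** - **Two grouping rules in SAP 2.1.** The first reads: "A treatment is defined by the dose level (corresponding to a single combination of doses of VAY736 and ibrutinib) and regimen". The second, two paragraphs on, reads: "Patients treated with the same dose level and schedule of VAY736 will be pooled, for all safety analyses including PK and ADA". The second adds that such a group may hold patients from both study parts.
- **Protocol pooling rule (opening text of Section 10).** "Patients treated with the same dose level and schedule of VAY736 will be pooled into a single treatment group". It applies to safety analysis and does not name PK; the SAP adds PK.
- **Ibrutinib dose.** Protocol 6.1.1: "During the dose escalation part of the study, the dose of ibrutinib will be 420 mg". Protocol 5.2, item 7: "Expansion: Patients may be on a dose of ibrutinib lower than 420 mg", if the dose has been stable for two months. Protocol 6.1.1 has expansion patients continue the dose they tolerated before enrolment.
- **Objective.** SAP Table 1-1 lists as secondary: "To characterize the PK of VAY736 and ibrutinib when used in combination therapy".
- **Ibrutinib PK outputs.** SAP 2.8.4: "For ibrutinib, PK parameters determined will be only AUClast, Cmax, Tmax, Tlast, and if applicable other PK parameters". Sections 2.8.4 to 2.8.4.3 name no split by ibrutinib dose and no dose-normalised parameter. The power model in 2.8.4.4 is for VAY736 only.

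**The concern.** Grouping by VAY736 dose and schedule suits VAY736 PK and anti-drug antibodies. It does not suit ibrutinib PK when ibrutinib dose varies within the group. Protocol 1.2.4.1.1 states that ibrutinib exposure rises with dose, so mixing doses moves the summary statistics and widens their spread.

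The mixing also lines up with VAY736 dose. Groups made up only of escalation patients are all assigned 420 mg; a group that also takes in expansion patients may not be. Someone reading ibrutinib exposure across VAY736 groups could take a lower value in the expansion dose group for an effect of VAY736 on ibrutinib, or could miss a real effect. Protocol 1.3.3 says that no specific interaction studies have been done and that the PK of both drugs will be monitored in this study, so these tables are the place where a reader would look.

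**Working it through.** The plan gives no sample size or precision figure for ibrutinib PK, so there is no figure to reproduce. The check is of the grouping text, followed by an illustration.

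**1. Apply each SAP 2.1 rule to one case.** Take two patients on the same VAY736 dose and schedule, one on ibrutinib 420 mg and one on less.
- Under the definition sentence they have different dose levels, hence different treatments.
- Under the pooling sentence they match on VAY736 dose level and schedule, hence fall in one group.

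Both cannot hold. The pooling sentence is the one that names PK, and nothing in 2.8.4 says which governs.

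**2. Which groups are exposed.** Escalation-only groups have no mixing of assigned ibrutinib doses. Only groups that include expansion patients are at risk.

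**3. Which samples are exposed.** Footnote a of Protocol Table 7-8 says that the need for the 0.5, 2 and 6 hour ibrutinib samples will be reassessed for expansion. If they are dropped, Cmax and AUClast come mainly from escalation patients at 420 mg. The pre-dose samples carry no such footnote, so concentration summaries by time point would still mix doses.

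**4. Illustrative size.** Let a share f of the pooled group take dose d below 420 mg, and let r = d/420. Assume dose-proportional exposure.
- Pooled geometric mean relative to 420 mg alone: r^f
- Pooled arithmetic mean relative to 420 mg alone: 1 − f + f·r
- Pooled log-variance: s² + f(1 − f)·(ln r)², with geometric CV = √(exp(variance) − 1)

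The values d = 280 or 140 mg, f = 10%, 25% or 50%, and a geometric CV of 60% (s² = ln 1.36 = 0.3075) are assumptions; none is in the documents.

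| d (mg) | f | Geometric mean ratio | Arithmetic mean ratio | Geometric CV (from 60%) |
|---|---|---|---|---|
| 280 | 10% | 0.960 | 0.967 | 61.7% |
| 280 | 25% | 0.904 | 0.917 | 63.4% |
| 280 | 50% | 0.816 | 0.833 | 64.6% |
| 140 | 10% | 0.896 | 0.933 | 71.8% |
| 140 | 25% | 0.760 | 0.833 | 84.0% |
| 140 | 50% | 0.577 | 0.667 | 91.6% |

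**5. A pool shaped like the plan.** Take the minimum of six escalation patients at the MTD/RDE (SAP 3.1.1), all at 420 mg, plus one expansion arm of 20 (SAP 3.1.2). If 10%, 25% or 50% of the 20 are below 420 mg, the shares of the pool are 2/26 = 0.077, 5/26 = 0.192 and 10/26 = 0.385. The geometric mean ratio is then 0.969, 0.925 and 0.856 at 280 mg, or 0.919, 0.810 and 0.655 at 140 mg.

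**6. After the fix.** Within a single ibrutinib dose, r = 1, so the ratio returns to 1.00 and the added log-variance to 0.

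**The case against.** The case on the other side has several parts.

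- **The objective is descriptive.** No test, target or contrast of ibrutinib exposure is planned, and there is no ibrutinib-alone arm. This stands, and it limits the harm to misreading of descriptive tables.
- **The definition sentence already separates the doses.** Under it, a lower-dose patient is a different treatment. But the later sentence names PK and groups on VAY736; the definition conflicts with it and does not override it.
- **Individual data remain.** PK parameters are listed per subject (SAP 2.8.4.3), individual profiles are plotted (Protocol 10.5.4), and all administered doses are listed (SAP 2.5.1.1.1). So the dose behind a value can be traced. That helps a careful reader but does not correct the summary tables, and the PK listing is not stated to show ibrutinib dose.
- **Within-patient trends are largely protected.** Patients enter on a stable dose and continue it, so mixed starting doses do not by themselves create a change over time. This stands. It does not help comparisons between VAY736 groups.
- **Mixing may not occur, or may be handled elsewhere.** The number of patients below 420 mg is not given, and the TFL shells, which are not available here, may split the tables. Both are fair, and both make the finding conditional.

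A reader might infer that the ibrutinib PK objective cannot be interpreted at all, or that averaging across ibrutinib doses is certain. The documents support neither: escalation-only groups are at an assigned 420 mg, individual data are reported, and the share on lower doses is unknown.

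**Conclusion.** The point holds as an internal conflict plus a missing rule. SAP 2.1 gives two incompatible groupings, and the one that names PK would combine ibrutinib doses in any group that includes expansion patients. Pooled ibrutinib summaries in those groups may be confounded by ibrutinib dose.

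The size cannot be established from the documents. The illustrated geometric mean ratios run from 0.96 to 0.58, that is, from negligible to large. They rest on assumed shares, assumed lower doses and dose-proportional exposure, while Protocol 1.2.4.1.1 says only that exposure increases with dose. VAY736 PK and anti-drug antibody summaries are not affected by this point, and it concerns analysis grouping only, not which dose patients should take.

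**What to change.** - **Reconcile the two sentences in SAP 2.1**, so that the grouping for ibrutinib PK is explicit.
- **In SAP 2.1 and 2.8.4, summarise ibrutinib concentrations and parameters by actual ibrutinib dose at sampling** (420 mg versus lower) within each VAY736 group.
- **Show ibrutinib dose in the PK listing.**
- **Use dose-normalised AUClast and Cmax only as a supplement**, with the proportionality assumption stated, because the documents do not establish it.
- **Keep VAY736 PK and ADA grouped by VAY736 dose and schedule.**

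This is a cheap improvement: a short SAP change, one extra table stratum and one listing column. No new data are needed, since SAP 2.5.1.3 records the ibrutinib dose on the ibrutinib PK eCRF and later changes in the change log. SAP Section 1 gives the route: an amendment before database lock, an addendum after it. The downside is small cells for the lower doses, where individual values may say more than summary statistics.

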2.1.1 General definitions

2.1.1.1 Investigational drug and study treatment

Investigational treatment will refer to the combination *VAY736 + ibrutinib*. The term investigational treatment may also be referred to as **study treatment**. For consistency across studies, the term study treatment will be used throughout this document.

The expression **combination therapy** may also be used to refer to the investigational treatment VAY736+ibrutinib, as defined in the protocol.

Investigational drug will refer to VAY736 and ibrutinib. The terms **investigational drug** and **study drug** are used interchangeably. For consistency across studies, the term study drug will be used throughout this document.

2.1.1.2 Date of first/last administration of study treatment

In the combination arm, the date of first (last) administration of study treatment is derived as the first (last) date when a non-zero dose of either VAY736 or ibrutinib was administered and recorded on the Dose Administration Record (DAR) eCRFs.

- First and last dose of VAY736 will be as recorded on the Study Treatment - VAY736) eCRF.
- First dose of ibrutinib will be as recorded on the Study Treatment - PK - Ibrutinib eCRF, and
- Last dose of ibrutinib will be as recorded on the Study Treatment – Ibrutinib eCRF.

2.1.1.3 Study day

The study day for **safety assessments** (e.g., adverse event onset, laboratory abnormality occurrence, vital sign measurement, dose interruption etc.) will be calculated as the difference between the date of the event (onset date of an event, assessment date etc.) and the start of study treatment plus 1. The first day of study treatment is therefore study day 1. Example: if start of study treatment is on 05-Jan-2014 and start date of an adverse event is on 09-Jan-2014 then the study day of the adverse event onset is 5. For safety assessments before start of study treatment, the study day is negative and derived by (date of event – start date of study treatment). For example: if start of study treatment is on 05-Jan-2014 and date of lab measurement is on 02-Jan-2014 then the study day of the laboratory abnormality is -3. Note, the day of start of study treatment is day 1, and the day before the date of first study treatment is day – 1, not day 0.

The study day for **other assessments** (e.g., efficacy, [REDACTED] etc.) will be calculated the same way as safety assessments.

2.1.1.4 Baseline

Baseline is the result of an investigation describing the “true” state before start of study treatment administration.

The last available assessment on or before the date of start of study treatment is taken as “baseline” assessment, unless specified otherwise. Assessments should be done within 21 days prior to the start of study treatment apart from baseline efficacy assessments which can be conducted within 28 days the date of start of study treatment. Height and virology assessments (including HBV and HCV) may also be performed outside of the 21-day window. Other assessments taken outside of the above specified assessment window, will not be considered for baseline.

In rare cases where multiple measurements meet the baseline definition, with no further flag or label that can identify the chronological order, then the following rule should be applied: If values are from central and local laboratories, the value from central assessment should be considered as baseline. If multiple values are from the same laboratory (local or central) or collected for ECGs or vital signs, then the last value should be considered as baseline.

For the purpose of VAY736 immunogenicity analysis, the baseline assessment will be defined with respect to the date of the first administration of VAY736.

If patients have no measurement meeting the above criteria, the baseline result will be missing.

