7.2.2.5.1 Hematology assessments

Hematology assessments in [Table 7-5](#) will be conducted at the time points listed below on the days outlined in [Table 7-1](#) or [Table 7-2](#), as appropriate for the VAY736 dosing regimen, within the windows outlined in [Section 7.1.3](#).

- C1D1: Pre-dose and 6 hours post-dose
- Remaining time points are collected as per the table. If the collection is on a treatment day, the sample is collected pre-dose.

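### SAP 2.1.1.4 intends a pre-dose laboratory baseline, but its date-based selection sentence, read literally, picks the 6-hour post-dose sample on Cycle 1 Day 1

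*SAP*

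**What the plan says.** SAP 2.1.1.4 opens with the concept: baseline is the "state before start of study treatment administration". The rule that a programmer would implement follows: "The last available assessment on or before the date of start of study treatment is taken as" baseline, unless specified otherwise. SAP 2.1.1.2 derives the start of study treatment as a date, without a clock time.

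Three further sentences of 2.1.1.4 bear on the choice:

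- A window: "Assessments should be done within 21 days prior to the start of study treatment", with exceptions for efficacy, height and virology.
- An exclusion: "Other assessments taken outside of the above specified assessment window, will not be considered for baseline".
- A tie-break for several qualifying values "with no further flag or label that can identify the chronological order". For values from the same laboratory, "then the last value should be considered as baseline".

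On study days, SAP 2.1.1.3 states: "The first day of study treatment is therefore study day 1".

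The protocol sets the sampling. For hematology (7.2.2.5.1) the schedule reads "C1D1: Pre-dose and 6 hours post-dose", and chemistry (7.2.2.5.2) is the same. On other treatment days the sample is taken pre-dose. Protocol 7.1 does not require screening assessments done within 3 days of C1D1 to be repeated on C1D1.

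**The concern.** The definition calls for a value untouched by the first infusion, while the selection sentence admits any value carrying the start date and takes the latest. Because the protocol schedules a 6-hour draw on that date, the two parts of the section point to different samples. The conflict is confined to C1D1, hematology and chemistry.

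Laboratory changes belong to the primary safety endpoint (SAP 2.6) and are tabulated as shifts from baseline to the worst post-baseline grade (SAP 2.8.2.3.1). A 6-hour baseline could absorb an early drug effect. This is most plausible for lymphocytes: Protocol 1.3.4 reports significant but transient falls after VAY736, resolved by the next scheduled evaluation at study day 7. The same section reports no VAY736-driven fall in neutrophils or hemoglobin.

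**Working it through.** No power, sample size or error-rate figure bears on this point, so the check has two parts: apply the written rule to an example patient, then see what a wrong choice does to a shift table.

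**1. Which sample does each reading select?** Assumed patient: screening sample on Day -7, first dose at 09:00 on C1D1, samples at 08:30 (pre-dose) and 15:00 (6 hours), next sample on C1D2.

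| Reading of SAP 2.1.1.4 | Sample selected |
|---|---|
| Selection sentence alone, by date | C1D1 6-hour post-dose |
| Opening definition (last sample before first administration) | C1D1 pre-dose |
| Selection sentence plus 21-day window by clock time | C1D1 pre-dose |
| Selection sentence plus window by calendar date, start date included | C1D1 6-hour post-dose |
| Selection sentence plus window by study day, Day 1 not counted as prior | Day -7 screening; both C1D1 samples drop out |

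The last reading also discards the valid pre-dose sample, which the selection sentence admits.

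*Variant.* If the C1D1 pre-dose draw is replaced by a sample on Day -2, as Protocol 7.1 allows, the 6-hour draw is the only sample on the start date. The date rule still selects it, and there is no same-day tie to break.

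*Same date or not.* The 6-hour sample falls on the next date only if the first dose is at 18:00 or later (18 + 6 = 24).

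**2. How many parameters?** SAP 2.8.2.3.1 lists 9 hematology and 23 chemistry parameters: 9 + 23 = 32. Protocol 1.3.4 reports an early fall after VAY736 for one of them, lymphocytes. This is not an upper bound: total white cells are also summarized and include lymphocytes.

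**3. Effect on the baseline grade.** Low-lymphocyte grades in SAP 5.3 (x10^9/L): at least 1.5 is grade 0; below 1.5 to 0.8 grade 1; below 0.8 to 0.5 grade 2; below 0.5 to 0.2 grade 3; below 0.2 grade 4. All patient values below are assumed. The pre-dose value is 1.6, grade 0.

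| 6-hour value | Baseline grade if the 6-hour value is used | Error against pre-dose grade 0 |
|---|---|---|
| 1.6 | 0 | 0 |
| 1.0 | 1 | 1 |
| 0.6 | 2 | 2 |
| 0.4 | 3 | 3 |
| 0.1 | 4 | 4 |

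**4. Effect on the shift.** Two cases, each with 1.6 pre-dose and 0.4 at 6 hours:

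- Later worst value 0.4 (grade 3): correct shift 0 to 3; literal shift 3 to 3.
- Later worst value 1.0 (grade 1): correct shift 0 to 3, because the 6-hour value counts as post-baseline; literal shift 3 to 1, an apparent improvement.

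The second case needs recovery before the later Cycle 1 draws. An effect that lasts beyond 6 hours still reaches the worst post-baseline column.

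**The case against.** Read as a whole, the section points to a pre-dose baseline. A 6-hour sample cannot meet the opening definition, the window looks backward from the start of treatment, and samples outside the window are excluded. Pre-dose and 6 hours post-dose are separately named time points, so the tie-break, meant for rare unlabelled cases, may never apply. The study-day reading is strained, since the selection sentence expressly admits the start date. Derived-variable rules sit in the programming specification, which may already be right.

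The effect size is also assumed throughout. Protocol 1.3.4 gives no 6-hour values and does not say that a fall is present at 6 hours. The 4-grade end needs a drop from 1.6 to 0.1, or 1.5/1.6 = about 94%. High-lymphocyte grades, relevant in CLL, are not modelled. Protocol 10.5.3.3 compares baseline with the worst on-treatment value, and SAP 2.1.1.5 starts the on-treatment period on the first-dose date. On that wording the 6-hour value also counts after baseline, and the second case becomes 3 to 3 instead of 3 to 1.

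Much of this stands: the intent is not in doubt, no programming error is shown, and the grade range is illustrative. The wording remains unsettled, however. The window removes the 6-hour sample only if read by clock time, while the start of treatment is derived as a date. The tie-break, where it applies, takes the later value. A C1D1 visit without a repeated pre-dose draw leaves only the 6-hour sample on that date. A result of 3 to 3 would still misstate the baseline cell and hide the fall.

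**Conclusion.** The concern holds and is minor. SAP 2.1.1.4 conflicts with itself for C1D1 hematology and chemistry, and its selection sentence applied literally yields a post-dose baseline. Confidence is high for the wording; whether the tables would be wrong depends on a programming specification that is not available.

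The possible error is confined to the baseline column of descriptive shift tables, and to the shifts read from it. Its size cannot be derived from the documents; the 0 to 4 grade range rests on assumed lymphocyte values. Grade 3/4 laboratory listings, adverse event reporting and the DLT and MTD analyses are unaffected. Lymphocytes for response assessment have their own wording, which places baseline before the start of treatment (SAP 5.2.2.1.3).

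**What to change.** Amend SAP 2.1.1.4 for hematology and chemistry on the date of first dose:

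- Only a sample labelled pre-dose can be baseline or, if samples are unlabelled, one collected before the first VAY736 infusion.
- Samples labelled 6 hours post-dose are always post-baseline.
- If there is no C1D1 pre-dose sample, baseline is the latest screening value in the 21-day window.

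The label comes first for two reasons. Protocol 7.2.3.1 requires exact draw times for PK samples, and no such statement is made for safety laboratories. Patients also enter already taking ibrutinib (Protocol 5.1), so a sample labelled pre-dose should not be lost because that morning's ibrutinib had already been taken. Anchoring unlabelled samples to the VAY736 infusion departs from the either-drug start in SAP 2.1.1.2, and the amendment should say so; it agrees with Protocol 7.1.2, which begins the treatment period at the first VAY736 dose given with ibrutinib.

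The cost is one or two sentences and a check that the programming specification agrees. After database lock the change would be made by addendum, as SAP section 1 provides. No new data are needed if the pre-dose and 6-hour labels are in the database, which the documents do not state. Unlabelled samples can be placed only if their collection times were recorded.
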